8.1.5 Overdose

An overdose is defined as the accidental or intentional administration of any dose of the product that is considered both excessive and medically important. All occurrences of medically significant overdose (suspected or confirmed and irrespective of whether or not it involved BHV-3241) must be communicated to Biohaven or a specified designee within 24 hours of the Investigator becoming aware and be fully documented as an SAE. An SAE is reported for overdose when the investigator feels the overdose was excessive and medically important. Details of any signs or symptoms and their management should be recorded including details of any antidote(s) administered.

8.1.6 Pregnancy

If, following initiation of the IP, it is discovered that a study subject is pregnant or may have been pregnant at the time of the IP exposure, including during at least 6 half-lives after IP administration, the IP will be permanently discontinued in an appropriate manner (i.e., dose tapering, if necessary, for patient safety). Protocol-required procedures for study discontinuation and follow up will be conducted unless contraindicated by the pregnancy (i.e., x-ray studies). Other appropriate pregnancy follow-up procedures should be considered if indicated.

Sites should instruct patients to contact the Investigator if they become pregnant during the course of the study. The Investigator must immediately notify **CCI** of the event within 24 hours of the Investigator becoming aware of the information and the site must complete a Pregnancy Report Form. Follow up information regarding the course of the pregnancy, including perinatal and neonatal outcome and, where applicable, offspring information must also be reported on a Pregnancy Report Form.

Any pregnancy that occurs in a female partner of a male study participant should also be reported to **CCI**.

8.1.7 Potential Drug Induced Liver Injury (DILI)

Wherever possible, timely confirmation of the initial liver-related laboratory abnormalities should occur prior to the reporting of a potential drug induced liver injury (DILI) event. All occurrences of potential DILIs, meeting the defined criteria, must be reported as SAEs as per Section 8.1.4.

Potential drug induced liver injury is defined as:

- Aminotransferases (ALT or AST) elevation > 3 times the ULN;
AND
- Total bilirubin (TBL) > 2 times ULN, without initial findings of cholestasis (elevated serum alkaline phosphatase);
AND
- No other immediately apparent possible causes of ALT or AST elevation and hyperbilirubinemia, including, but not limited to, viral hepatitis, pre-existing chronic or acute liver disease, or the administration of other drug(s) known to be hepatotoxic.

If any potential DILI is identified and meets the criteria above, the Biohaven Medical Monitor should immediately be contacted for further instruction on dosing adjustments and whether the patient must discontinue from the trial and appropriate follow up requirements.

8.1.8 Adverse Event of Special Interest-Thyroid Function

Reversible changes in thyroid function tests were observed during the preclinical studies and clinical studies with BHV-3241. Physical examination and laboratory monitoring of thyroid function with serum triiodothyronine (free T3), thyroxine (free T4), TSH, and anti TPO antibodies will be performed and documented throughout this study. Any significant abnormal findings should be discussed with the study Medical Monitor and maybe followed up as per local practice (e.g., investigations and consultation with endocrinologist).

In cases of suspected hypothyroidism, repeat thyroid function tests should be measured and thyroxine replacement therapy should be considered. Initiation of treatment is at the discretion of the Investigator. Potential initiation of thyroxine replacement therapy may be considered according to the following guidelines:

- Mild TSH increase: 5.0 to 10 mU/L (assuming a normal TSH range of 0.4 to 4.9 mU/L) and unchanged free T4 (and/or free T3)
 - With clinical symptoms of hypothyroidism: Consider thyroxine treatment if confirmed at 2 consecutive occasions and not explained by concomitant illness/fever/infection/surgery

- No symptoms: Continue normal monitoring.
- TSH greater than the ULN and decreased free T4 (and/or free T3) below normal range:
 - Regardless of symptoms, consider initiation of thyroxine treatment if confirmed at 2 consecutive occasions and not explained by concomitant illness/fever/ infection/surgery (if severe symptoms, repeat sampling in 2 weeks).

If signs/symptoms of hypothyroidism and/or significant changes in thyroid hormone levels (free T3/free T4/TSH) develop, collection of follow up clinical chemistry samples and/or unscheduled study visits may be warranted.

Clinically significant laboratory abnormalities will be identified as Grade 3 to 4 laboratory test results graded according to numeric laboratory test criteria in Common Terminology Criteria for Adverse Events (CTCAE) Version 5.0 (2017)¹⁸. For those not available in CTCAE, according to Division of AIDS (DAIDS) Table for Grading the Severity of Adult and Pediatric Adverse Events Corrected Version 2.1 (2017)¹⁹.

If there are clinically significant issues with tolerability that are not able to be treated adequately with thyroxine replacement therapy, the Investigator may consider modifications to the dosage regimen. Consultation with the Medical Monitor is required. Modifications may include reducing the dose of BHV-3241/matching placebo to 300 mg BID or taking a dose holiday. Any such modifications to the dosage regimen should be noted in the CRF.

8.2 Non-serious Adverse Events

A non-serious adverse event is an AE not classified as a SAE.

8.2.1 Collection and Reporting of Non-Serious Adverse Events

The collection of non-serious AE information should begin at the initiation of study drug.

Non-serious adverse events should be followed until conclusion or stabilization, or reported as SAEs if they become serious. Follow-up is required for non-serious AEs that cause interruption or discontinuation of study drug or those that are present at the end of study treatment.

8.2.2 Laboratory Test Abnormalities

The following laboratory test abnormalities should be captured on the non-serious AE CRF page or SAE Report Form (paper or electronic) as appropriate:

- Any laboratory test result that is clinically significant or meets the definition of an SAE;
- Any laboratory abnormality that required the patient to have the study drug discontinued or interrupted;
- Any laboratory abnormality that required the patient to receive specific corrective therapy.

9 STATISTICS

Detailed plans for analysis are summarized in a separate Statistical Analysis Plan (SAP) document. A summary of statistical aspects of the design and intended analysis is provided here.

9.1 General Procedures

Categorical variables are tabulated with counts and percentages. Continuous variables are summarized with univariate statistics (e.g., n, mean, standard error, median, minimum and maximum).

For the calculation of descriptive statistics of observed data, subjects must have a baseline value to be evaluable for endpoints based on values and changes from baseline over time.

Tabulations of the following endpoints present the number of unique subjects with an event: protocol deviations; non-study medications; adverse events; and laboratory abnormalities. Thus, for these endpoints, multiple occurrences of the same event are counted only once per subject.

9.2 Sample Size

The sample size for this study will be approximately 325 randomized subjects. Based on unpublished data from the Promesa study, studying EGCG (epigallocatechingallate) vs placebo²⁶ with a treatment duration of 48 weeks, the placebo group had a 4.88 point increase with a standard deviation of 4.85 in the modified UMSARS Part I and Part II total score. With an expected improvement of 40% at Week 48 for BHV-3241 compared to placebo, a total of 260 subjects (130 per group) provides 90% power based on a 2-sample, two-sided t-test. With a drop-out rate of ~20%, the study will randomize approximately 325 subjects.

9.3 Populations for Analysis

The population of interest, for all estimands, are subjects diagnosed with possible or probable MSA.

The following analysis sets are defined for this protocol:

Enrolled subjects: Subjects who signed an informed consent form and were assigned a Patient Identification number (PID).

Randomized subjects: Enrolled subjects who received a treatment assignment from the Interactive Web Response System (IWRS).

Treated/Safety: Enrolled subjects who received at least 1 dose of blinded study therapy (BHV-3241 or placebo).

Modified Intent to Treat (mITT) subjects: Randomized subjects that received at least one dose of blinded study therapy and provided a baseline and at least one post-baseline efficacy assessment.

Open-Label Extension Treated subjects: Enrolled subjects in the extension phase who received at least 1 dose of open-label study therapy (BHV-3241).

BHV-3241 Treated Participants: Enrolled subjects who received at least 1 dose of BHV-3241 (blinded or open-label).

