9.4.5 Adjustment for Multiplicity

Type-1 error will be controlled for the primary and key secondary efficacy endpoints by testing them with a gate-keeping procedure. The primary endpoint will be tested at a two-sided alpha level of 0.05. If this test is significant, then the key secondary efficacy endpoints will be tested using Hochberg's procedure. If the test of the primary endpoint is not significant, then the unadjusted p-values for the key secondary endpoints will be presented only for descriptive purposes.

No attempt will be made to adjust for multiplicity when testing the non-key secondary or CCI endpoints. Any endpoints subjected to significance testing are evaluated at an unadjusted two-sided alpha level of 0.05.

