3.2.1 Primary Objective Estimand

The estimands corresponding to the primary objectives for this study are shown in Table 1.

Table 1: Primary Objective Estimands

Objective	To evaluate the efficacy of Verdiperstat, compared to placebo, as measured by a change from baseline in a modified UMSARS score at Week 48
Efficacy Endpoint	Change from baseline in a modified UMSARS score at Week 48
Summary	Using the mITT population:
	 Descriptive statistics for modified UMSARS score and change from baseline as a continuous variable by treatment group at each visit
	 Difference in mean change from baseline in modified UMSARS scores between treatment groups at week 48 estimated and tested using a mixed-effect model for repeated measures (MMRM)
Intercurrent	1) Main Analysis - Observed data only
Events	2) Supplementary Analysis 1 – While on-treatment strategy
	3) Supplementary Analysis 2 – Compliant subjects hypothetical strategy
	4) Sensitivity Analysis – Multiple imputation jump to reference and copy increment from reference
	5) Sensitivity Analysis – Observed data only using narrower visit window for Week 48
Objective	To assess the safety and tolerability of Verdiperstat, relative to placebo, in subjects with MSA
Safety Endpoint	Frequency of unique subjects with serious adverse events (SAEs), AEs leading to study drug discontinuation, AEs related to study drug, clinically significant ECG abnormalities, and clinically significant laboratory test abnormalities
Summary	Number and percentage of subjects with safety events and findings for the safety population
Intercurrent Events	Treatment policy strategy, i.e., no accounting for intercurrent event

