6.3 Efficacy

Unless otherwise noted, the primary and secondary efficacy analyses will be conducted on the mITT population. All efficacy data will be included in listings by subject, treatment group, and visit (as applicable). When applicable, the efficacy analyses will be presented for the double-blind and OLE phases, separately and combined. For the OLE phase, no inferential statistics will be derived.

For the double-blind phase, baseline is considered as the last available assessment on or before the first day of study treatment. For the OLE Phase, baseline is considered as (1) the double-blind Week 48 visit assessment for subjects who have been off of the study drug for less than or equal to 4 weeks, or (2) the OLE Baseline-Extension visit assessment for subjects who have been off of the study drug for greater than 4 weeks.

Table 4: Primary, Secondary, and COL Efficacy Estimands and Analyses

Index	Description	Variable Type	Treatment Group Comparison	On-Study Data
Prima	ry Estimand			
P01	Difference between treatment groups in change from baseline in the modified UMSARS scores at Week 48 of the DB Phase	Continuous	MMRM	Screening, Baseline, Weeks 4, 12, 24, 36, 48,
Second	lary Estimand			
S01	Difference between treatment groups in change from baseline in CGI-I score at Week 48 of the DB Phase	Continuous	MMRM	Weeks 4, 12, 24, 36, 48
S02	Difference between treatment groups in change from baseline in MSA-QoL motor subscales score at Week 48 of the DB Phase	Continuous	MMRM	Baseline, Weeks 24, 48, Baseline Ext, Weeks 12 Ext, 24 Ext, 36 Ext, 48 Ext
S03	Difference between treatment groups in change from baseline in MSA-QoL non-motor subscales score at Week 48 of the DB Phase	Continuous	MMRM	Baseline, Weeks 24, 48, Baseline Ext, Weeks 12 Ext, 24 Ext, 36 Ext, 48 Ext
S04	Difference between treatment groups in change from baseline in UMSARS Part I and II total score at Week 48 of the DB Phase	Continuous	MMRM	Screening, Baseline, Weeks 4, 12, 24, 36, 48, Baseline Ext, Weeks 12 Ext, 24 Ext, 36 Ext, 48 Ext
S05	Difference between treatment groups in change from baseline in PGI-S score at Week 48 of the DB Phase	Continuous	MMRM	Baseline, Weeks 4, 12, 24, 36, 48
S06	Difference between treatment groups in change from baseline in CGI-S score at Week 48 of the DB Phase	Continuous	MMRM	Baseline, Weeks 4, 12, 24, 36, 48

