6.3.2.3 Sensitivity Analyses

For the primary endpoint, sensitivity analyses using multiple imputation (MI) will be conducted using a copy increment from reference and jump to reference approach to assess the impact of the MAR assumption of the analysis model used.

The primary analysis of the modified UMSARS score based on a MMRM model assumes that data is MAR and subjects who discontinue study medication prematurely have a response profile for the remainder of the treatment phase similar to subjects who completed the 48 weeks of the treatment phase (an analysis of a "de jure" or "hypothetical" based estimand). In order to explore the impact of these assumptions, a sensitivity analysis will be conducted where subjects who discontinue Verdiperstat prematurely have a response profile similar to those subjects on placebo using both a copy increment from reference and jump to reference approach. These analyses use a "defacto" estimand and are based on the methods described in.³

Mean changes from baseline in the modified UMSARS score will be analyzed based on data observed while the subject remains on study as well as data imputed using MI methodology for time points at which no value is observed. MI will be performed under the assumption of MAR and will be implemented in two steps. In the first step, a parameter-estimation model is fitted assuming MAR by a Markov chain Monte Carlo (MCMC) procedure in SAS with starting values based on fitting an MMRM model with the MIXED procedure. In the second step, an imputation model, which uses the parameters estimated in part 1, calculates predicted values for each pattern of withdrawal. Any intermediate missing values are imputed first assuming MAR, and then MNAR (missing not at random); part of the model is used to impute values for trailing missing values (e.g. after subject withdrawal from study). The MNAR part of the imputation will use a profile based on the estimated profile of the reference arm (placebo) to impute values after withdrawal for subjects in the Verdiperstat arm. In the case of the jump to reference approach, the mean response distribution after withdrawal will be used; and for the copy increment from reference, the mean increments will follow those from the placebo arm after withdrawal. Subjects in the placebo arm will use the profile under MAR.

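### The reference-based sensitivity analyses run on mITT, so treated verdiperstat subjects with no post-baseline efficacy assessment are dropped rather than given the placebo course; a favourable estimate is inflated by 1/(1-f), probably slightly

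*Protocol*

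**What the plan says.** Protocol 9.3 defines the mITT set as "Randomized subjects that received at least one dose of blinded study therapy and provided a baseline and at least one post-baseline efficacy assessment"; SAP 4.1 repeats the definition. SAP 6.3 states: "Unless otherwise noted, the primary and secondary efficacy analyses will be conducted on the mITT population". SAP Table 1 (section 3.2.1) puts the primary efficacy summary on mITT and lists below it "Sensitivity Analysis – Multiple imputation jump to reference and copy increment from reference". SAP 6.3.2.3, which describes the imputation, names no other set. It gives the purpose: "a sensitivity analysis will be conducted where subjects who discontinue Verdiperstat prematurely have a response profile similar to those subjects on placebo". Placebo subjects with missing data are imputed under MAR.

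Three further provisions bear on who falls outside mITT. The first scheduled post-baseline UMSARS is at Week 4 (Protocol Table 1 and 6.2.3.1). Subjects who stop drug before Week 48 are to have an Early Discontinuation visit, which shares the Week 48 column of Protocol Table 1 and so includes the efficacy scales. SAP 6.2.1 tabulates mITT exclusions by treatment group.

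**The concern.** Membership of mITT depends on something that happens after randomization. In the MMRM this does no harm, because a subject with only a baseline contributes no change score. In J2R and CIR it matters. These analyses exist to replace the MAR assumption with a placebo-like course for verdiperstat subjects who leave. For a subject with no post-baseline value there is no earlier benefit to retain, so both methods would assign the placebo course, that is, no drug effect. Leaving the subject out implicitly assigns the average effect of those who remain.

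The entry rule also turns on something unrelated to the endpoint. It asks for any efficacy assessment, not a modified UMSARS score. Two subjects with the same UMSARS information, baseline only, are treated differently if one of them completed a single PGI-S.

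At stake is the size of the two analyses that SAP 6.3.2.3 offers as its check on MAR. Any error runs in one direction: it makes a favourable result look more robust.

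**Working it through.** **1. The plan's own figures.** Inputs from Protocol 9.2 and 9.4.5: "the placebo group had a 4.88 point increase with a standard deviation of 4.85"; "With an expected improvement of 40% at Week 48 for BHV-3241 compared to placebo"; "The primary endpoint will be tested at a two-sided alpha level of 0.05"; "a total of 260 subjects (130 per group) provides 90% power based on a 2-sample, two-sided t-test".

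- Effect = 0.40 × 4.88 = 1.952 points.
- n per arm = 2 × (1.960 + 1.282)² × 4.85² / 1.952² = 129.7, so 130. Power at 130 per arm is 0.901 (normal approximation) or 0.898 (t-test).
- 260 / (1 - 0.20) = 325.

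The design reproduces.

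**2. The effect of the exclusion.** Let f be the share of the active arm with no post-baseline efficacy assessment. Under J2R and CIR these subjects have zero expected drug effect. Excluded placebo subjects imputed under MAR leave the placebo mean unchanged, so nothing cancels. Hence

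effect (all treated) = (1 - f) × effect (mITT) + f × 0,

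and the mITT estimate is larger by the factor 1/(1 - f).

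**3. A value for f.** The documents give none. If the planned 20% drop-out is spread evenly over 48 weeks, the share gone before Week 4 is 0.20 × 4/48 = 1.67%, or 0.0167 × 162.5 = 2.7 active-arm subjects. This supposes that none of them attends an Early Discontinuation visit. The ceiling is 20% (every drop-out unassessed).

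**4. Size.** Assume a drug effect that grows linearly to 1.952 points, with 20% drop-out in total.

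- J2R, all treated: only completers keep the effect, so 0.80 × 1.952 = 1.562 whatever f is.
- CIR, all treated: later drop-outs keep what they had gained. Take the last score at Week 4, 12, 24 or 36 in proportion 8:12:12:12 (the lengths of the intervals that follow). The mean share kept is (8×4 + 12×12 + 12×24 + 12×36) / (44 × 48) = 896/2112 = 0.424. The effect is 1.952 × [0.80 + (0.20 - f) × 0.424].
- mITT: divide each by (1 - f).

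| f | Active-arm subjects | J2R all treated | J2R mITT | Shift | CIR all treated | CIR mITT | Shift |
|---|---|---|---|---|---|---|---|
| 0.5% | 0.8 | 1.562 | 1.569 | 0.008 | 1.723 | 1.732 | 0.009 |
| 1.67% | 2.7 | 1.562 | 1.588 | 0.026 | 1.713 | 1.742 | 0.029 |
| 5% | 8.1 | 1.562 | 1.644 | 0.082 | 1.686 | 1.775 | 0.089 |
| 10% | about 16 | 1.562 | 1.735 | 0.174 | 1.644 | 1.827 | 0.183 |
| 20% (ceiling) | 32.5 | 1.562 | 1.952 | 0.390 | 1.562 | 1.952 | 0.390 |

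A simulation of 1,000,000 active-arm subjects at f = 1.67% agrees: J2R 1.587 against 1.561, CIR 1.741 against 1.712.

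**5. Against the noise.** The design standard error is 4.85 × √(2/130) = 0.60. At f = 1.67% the shift is under 5% of one standard error; at 5% it is about 0.14 to 0.15 of one. With that standard error held fixed, the chance of a significant J2R result is 0.752 on mITT against 0.738 on all treated at f = 1.67%, and 0.780 against 0.738 at f = 5%.

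**The case against.** The best reply is that few subjects will be excluded. A subject who stops during titration and attends the Early Discontinuation visit has efficacy scales recorded, enters mITT and is imputed. UMSARS Part I may be done remotely under the COVID-19 provisions. Read literally, even the Week 48 phone call could qualify a subject, because it collects time-to-event measures that Protocol Table 1 lists among the efficacy assessments. All of this stands. A reader might infer that the earliest drop-outs as a class are never imputed; the documents do not say that. The gap is confined to treated subjects with no assessment at all, for example those who withdraw consent for every procedure (exempted in Protocol 6.4), are lost, or die first.

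A reader might also take f to be near 7%, because the Phase 2 MSA study lost 13 of 59 by Week 12 (22% × 4/12 = 7.3%). That equates leaving before Week 4 with having no assessment. It would also place 7.3 of the planned 20 points, or 37% of all drop-out, in the first 4 of 48 weeks. The plan supports neither step.

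Nor do the documents show that early loss is caused by the drug. In that study 3 of 20 were lost at 600 mg, 5 of 19 at 300 mg and 5 of 20 on placebo. The numbers are small, but they do not point that way.

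Two other replies carry less weight. Tabulating mITT exclusions (SAP 6.2.1) shows how many there were but leaves the reported estimate as it is. Imputing a Week 48 score after death is a debatable estimand choice, but 6.3.2.3 gives no separate rule for death, so the question arises equally for subjects who die after a first score.

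**Conclusion.** The point holds in a limited form. By the SAP default and Table 1, J2R and CIR omit treated verdiperstat subjects who have no post-baseline efficacy assessment, and a favourable estimate is then too large by 1/(1 - f) relative to an analysis of all treated subjects. With the planned drop-out spread evenly and nobody assessed before Week 4, that is about 0.03 points on an effect of about 1.6 to 1.7. It becomes noticeable only at about f = 5%, where it is 0.08 to 0.09 points. These figures rest on the plan's effect and drop-out rate, a linear course, and a value of f that the documents do not give.

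A reader might infer that both sensitivity estimates are bound to be too favourable. That does not follow: if no active-arm subject is excluded there is no shift, and if the estimate does not favour the drug the factor does not make it favourable. No confirmatory result is touched; the primary MMRM and the Hochberg tests do not use the imputation. This is a cheap improvement to the check on MAR, not a flaw in the primary analysis.

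**What to change.** In SAP 6.3.2.3 and Table 1, state that J2R and CIR are run on all randomized and treated subjects with a baseline modified UMSARS, whether or not they have a post-baseline score. Impute verdiperstat subjects with no post-baseline value from the placebo profile given baseline, and such placebo subjects under MAR. Keep mITT for the MMRM.

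The imputation model already contains baseline and its interaction with visit (SAP 6.3.2.3), so subjects with only a baseline can be imputed without a new model. The cost is one sentence of text and a slightly less favourable sensitivity estimate.

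In the same edit, SAP 6.2.1 should be tidied: it refers to mITT subjects outside an efficacy analysis set that SAP 4.1 does not define.
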